3.2.2 Subject Disposition

The number of subjects screened, the number and percentage of screen failures, and their primary reason for screen failure will be summarized.

Subject disposition will be summarized by treatment groups for all randomized subjects. The number and percentage of subjects who completed or prematurely terminated from the treatment phase and from the study will be summarized separately by their primary reason for termination for each treatment group.

In addition, the number and percentage of randomized subjects who continued into Period 1 and Period 2 will be summarized by treatment group. The number and percentage of randomized subjects will be summarized by region, country, and sites for each treatment group. The number and percentage of randomized subjects in each of the study populations will also be presented.

3.2.3 Protocol Deviations

Protocol deviations will be identified, reviewed and documented by the clinical team prior to database lock/treatment unblinding. All protocol deviations will be categorized according to major/minor and standard classifications including but not limited to the following:

- Violations of inclusion/exclusion criteria
- Noncompliance with or incorrect implementation of protocol procedures
- Noncompliance of randomized study drug and dosage
- Use of prohibited concomitant medication

Major protocol deviations will be summarized by category and treatment group.

3.2.4 Demographic and Other Baseline Characteristics

Demographic and other baseline characteristics for FAS, Safety Analysis Set and On-Treatment Safety Analysis Set will be summarized for each treatment group using descriptive

statistics. Continuous demographic and baseline variables include age, height, weight, and BMI; categorical variables include sex, age group (< 65, 65 to < 75, ≥75), BMI group (<18.5, 18.5 to <25, 25 to 30, >30), region (North America, Europe and New Zealand, Asia), race, and ethnicity.

The selected baseline assessments of Sleep Diary variables including sSOL, sWASO, sSE, sTST, sTIB, number of awakenings, quality of sleep, morning sleepiness; ISI total score and its individual question score; FSS will be summarized by treatment group. The BDI-II and BAI scores measured at screening will also be summarized.

3.2.4.1 Medical History

All medical histories as documented by the Medical History and Current Medical Conditions eCRF will be coded using the Medical Dictionary for Regulatory Activities (MedDRA).

The number and percent of subjects with medical history will be summarized by System Organ Class (SOC), preferred term for each treatment group based on Safety Analysis Set. A subject data listing of medical history and current medical conditions will be provided.

3.2.5 Prior and Concomitant Therapy

All investigator terms for medications recorded in the eCRF will be coded to an 11-digit code using the World Health Organization Drug Dictionary (WHO DD; Mar 2017 or latest version). If the Safety Analysis Set and FAS differ, then the prior and concomitant medication summaries will be repeated on the FAS.

Prior medications are defined as medications that stopped before the first dose of study drug, where study drug includes placebo during the Run-In Period.

Concomitant medications are defined as medications that (1) started before the first dose of study drug (including placebo Run-In Period) and are continuing at the time of the first dose of study drug, or (2) started on or after the date of the first dose of study drug (including the placebo Run-In Period) to the last dose day plus 14 days.

For the Run-In Period, a concomitant medication is defined as a medication that started on or before the 1st dose of study medication of the Run-In Period and continued during the Run-In Period, or started during the Run-In Period. For Period 1, a concomitant medication is defined as a medication that started on or before the 1st dose of study medication of Period 1 and continued during Period 1, or started during Period 1. For Period 2, a concomitant medication is defined as a medication that started on or before the 1st dose of study medication in Period 2 and continued during Period 2, or started during Period 2.

The number (percentage) of subjects who take prior and concomitant medications will be summarized on the Safety Analysis Set by treatment group, Anatomical Therapeutic Chemical class (ATC) and World Health Organization Drug Dictionary-preferred term (PT). If the Safety Analysis Set and FAS differ, then the prior and concomitant medication summaries will be repeated on the FAS.

If the subject has taken the same concomitant medication (as coded to preferred WHO-drug term) more than once, the subject will be counted only once in the tabulation.

Separate summaries of concomitant medications will be provided for Run-in Period (using Safety Analysis Set), Period 1 (using Safety Analysis Set), Period 2 (using On-Treatment Safety Analysis Set) and Period 1 plus Period 2 (using On-Treatment Safety Analysis Set).

3.2.6 Treatment Compliance

Treatment compliance (in %) for each study drug will be calculated on the basis of number of tablets dispensed, lost and returned, separately for each type of tablet, for all randomized subjects as follows:

$$\frac{100 \times (\text{total number of tablets dispensed} - \text{total number of tablets returned or lost})}{\text{number of tablets expected to be taken}}$$

Treatment compliance will be summarized using descriptive summary statistics and number (percentage) of subjects using the categories <80%, ≥ 80% to ≤100%, >100% to ≤ 120%, and > 120% for each treatment group. Separate summaries will be provided for Run-in Period (using Safety Analysis Set), Treatment Period 1 (using Safety Analysis Set), and Treatment Period 2 (using On-Treatment Safety Analysis Set).

3.3 Data Analysis General Considerations

The FAS will be used as the primary population for all efficacy analyses. The Per Protocol analysis set will be used for sensitivity analyses to corroborate the primary efficacy endpoints.

3.3.1 Pooling of Centers

This study was a multicenter, international study with an estimated 120 centers participating in the study. Due to small expected number of subjects in each center, sites will be pooled within specific regions for primary and secondary efficacy analyses. Other analyses will be performed with all centers pooled across the study unless stated otherwise. Consistency of results across regions (North America, Europe and New Zealand, Asia) will be examined as specified in the respective sections in this document.

3.3.2 Adjustments for Covariates

Baseline assessment, region, and age groups are used as covariates in the primary and secondary analyses.

3.3.3 Multiple Comparisons/Multiplicity

A sequential gate-keeping procedure will be used for primary endpoint and secondary endpoint comparisons to control for the overall type 1 error at the 0.05 significance level. The first endpoint comparison will be tested at the 0.05 significance level. If the testing is

found to be statistical significant, then proceed to the next endpoint testing at significance level of 0.05, otherwise stop testing.

The primary endpoints will be tested in the following order:

- Change from Study Baseline at Month 6 in sSOL, LEM10 compared to PBO
- Change from Study Baseline at Month 6 in sSOL, LEM5 compared to PBO

The key secondary endpoints will only be tested if both primary analyses are statistically significant at the 0.05 level. The key secondary endpoints will be tested in the following order:

- Change from Study Baseline at Month 6 in sSE, LEM10 compared to PBO
- Change from Study Baseline at Month 6 in sSE, LEM5 compared to PBO
- Change from Study Baseline at Month 6 in sWASO, LEM10 compared to PBO
- Change from Study Baseline at Month 6 in sWASO, LEM5 compared to PBO

No multiplicity testing will be performed for other secondary or exploratory endpoints.

3.3.4 Examination of Subgroups

Subgroup analysis of primary and key-secondary efficacy endpoints will be performed using age group (< 65, 65 to < 75, ≥ 75), sex (male and female), race (white, black, Asian, and other), region, and BMI group (< 18.5, ≥ 18.5 to < 25, ≥ 25 to 30, and > 30) as detailed in [Section 3.4](#) and [Section 3.6](#).

3.3.5 Handling of Missing Data, Dropouts, and Outliers

This study collected sleep diary data directly from subjects via a vendor-provided hand-held device; it is possible that some values entered by subjects may have resulted from input errors. For example, it is not possible for a total waketime to be longer than the time the subject spends in bed for the night. In such cases, erroneous data will be considered as missing values in data analyses. Efficacy data handling will be mentioned in the [Section 6.1](#).

The primary and key secondary efficacy endpoints will be analyzed using mixed effect model repeated measurement analysis (MMRM), the missing values will be imputed using pattern-mixture multiple imputation (MI) assuming the missing data is missing not at random (MNAR) utilizing the complete case missing value pattern (CCMV). Additional sensitivity analyses will also be performed on primary and key secondary efficacy endpoints as follows:

Table 3 Multiple Imputation Methods

MI Methods	Assumption	Analysis Type																																																																
Complete Case Missing Value (CCMV)	Subjects with missing data at any day have a similar distribution as the completers within the respective treatment group (Pattern 1, below), where completers are defined as having no missing assessments for any post-baseline visits	Primary																																																																
Complete Case-7 CCMV(k=7)	
This MI method will use all available monotone missing patterns to impute missing data assuming MNAR. This will relax the assumption of using only the complete cases as in the primary analysis.
 
  
 Timepoints where results are available	Wk1	M1	M2	M3	M4	M5	M6	
   
 Pattern 1	x	x	x	x	x	x	x	
 
 Pattern 2	x	x	x	x	x	x	.	
 
 Pattern 3	x	x	x	x	x	.	.	
 
 Pattern 4	x	x	x	x	.	.	.	
 
 Pattern 5	x	x	x	.	.	.	.	
 
 Pattern 6	x	x	.	.	.	.	.	
 
 Pattern 7	x	.	.	.	.	.	.	
  
 
Wk1=week1; M1=month1; M2=month2; M3=month3; M4=month4; M5=month5; M6=month6; x=observed data; .=missing data
	Timepoints where results are available	Wk1	M1	M2	M3	M4	M5	M6	Pattern 1	x	x	x	x	x	x	x	Pattern 2	x	x	x	x	x	x	.	Pattern 3	x	x	x	x	x	.	.	Pattern 4	x	x	x	x	.	.	.	Pattern 5	x	x	x	Pattern 6	x	x	Pattern 7	x	Sensitivity
Timepoints where results are available	Wk1	M1	M2	M3	M4	M5	M6																																																											
Pattern 1	x	x	x	x	x	x	x																																																											
Pattern 2	x	x	x	x	x	x	.																																																											
Pattern 3	x	x	x	x	x	.	.																																																											
Pattern 4	x	x	x	x	.	.	.																																																											
Pattern 5	x	x	x																																																											
Pattern 6	x	x																																																											
Pattern 7	x																																																											
Tipping Point	Imputation towards the null hypotheses: A range of shifts starting from the primary analysis (CCMV) will be used in the multiple imputation of missing data assuming MNAR to identify the specific shift and treatment effect that will tip the results from statistically significant to non-significant.	Sensitivity																																																																
Tipping Point	Imputation towards the null hypotheses: A range of shifts will be used in the multiple imputation of missing data assuming MAR to identify the specific shift and treatment effect that will tip the results from statistically significant to non-significant.	Sensitivity																																																																

Unless stated otherwise, missing values will be considered as non-responders in responder analyses and the continuous variables will be analyzed using MMRM assuming MAR. Details can be found in [Section 3.4](#).

All safety analyses will be performed based on the observed data only.

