9.7.1.6.1 ANALYSIS FOR THE PRIMARY ENDPOINT

Null Hypothesis: For sSOL, no difference exists in the mean change from Study Baseline to Month 6 of treatment with LEM10 and LEM5 as compared with PBO.

Alternative Hypothesis: For sSOL, a difference exists in the mean change from Study Baseline to Month 6 for LEM10 and LEM5 as compared with PBO.

The sSOL change from Study Baseline to Month 6 will be analyzed using the mixed effect model repeated measurement (MMRM) analysis on the FAS. The model will include all data and will be adjusted for the corresponding Study Baseline value, region, age group (<65 years old, ≥65 years old), treatment, time (average of the first 7 nights, Month 1, Month 3, and Month 6) and the interaction of treatment by time. An unstructured covariance matrix will be used, and if the model fails to converge, then an autoregressive matrix will be used. The missing values will be imputed using a pattern mixture model utilizing multiple imputation (MI) assuming the missing values are missing not at random (MNAR) utilizing the complete case missing value pattern (CCMV - subjects who completed all primary efficacy assessments without missing values). (revised per Amendment 04) The missing values for a given visit will be imputed using all available values including the retrieved measurement from the post-discontinuation data. The treatment comparison will be performed using contrasts. The p-value, least square (LS) means and the 95% confidence interval (CI) for the treatment difference will also be provided. Details of pattern mixture model and MI method will be presented in SAP. (revised per Amendment 03)

The following analyses will be considered as sensitivity analyses (revised per Amendment 04):

- Missing imputation assuming MNAR utilizing CCMV-7: The same MMRM method used in the primary analysis will be applied utilizing CCMV-7 (ie, up to 7 monotone missing patterns will be used for missing value imputation). (revised per Amendment 04)
- Tipping point analysis: A range of shifts starting from the primary analysis (CCMV) will be used in the multiple imputation of missing data assuming MNAR to identify the specific shift and treatment effect that will tip the results from statistically significant to non-significant. (revised per Amendment 04)

The following analyses will be considered as supplementary analyses (revised per Amendment 04):

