3.3.6 Other Considerations

The following estimands are evaluated for the primary efficacy endpoint (change from baseline in mean sSOL on Month 6) in this study ([Mallinckrodt, et al., 2012](#), and [ICH, E9\(R1\) Final Concept Paper, 2014](#)). The details of the analysis method are discussed in [Section 3.4](#).

Table 4 Estimands

Estimand	Description	Population	Intervention Effect of Interest	Analysis Type
Difference in outcome improvement for all randomized subjects	- all randomized subjects regardless of the treatment subjects actually received - include data after dropout	FAS	missing values imputed using MI assuming MNAR utilizing CCMV missing value pattern (complete cases) (Assumes the probability of missing observations for any subject depends on the unobserved events. For the missing pattern, complete cases will be used in the imputation. Thus this method assumes dropouts or subjects with missing values have similar treatment effect as the completers within the respective treatment group.)	primary
Difference in outcome improvement for all randomized subjects	- all randomized subjects regardless of what treatment subjects actually received - include data after dropout	FAS	missing values imputed using MI assuming MNAR utilizing CCMV-7 missing value pattern (all available up to 7 monotone missing patterns) (Assumes the probability of missing observations for any subject depends on the unobserved events. For the missing pattern, complete cases up to 7 monotone missing patterns will be used in the imputation – see Section 3.4.1.3 for details. Thus this method relaxes the assumption of the primary analysis of using only completers to impute the missing data.)	Sensitivity (CCMV-7)
Difference in outcome improvement for all randomized subjects	- all randomized subjects regardless of what treatment subjects actually received - include data after dropout	FAS	a range of shifts starting from the primary analysis (CCMV) will be used in the multiple imputation of missing data assuming MNAR to identify the specific shift and treatment effect that will tip the results from statistically significant to non-significant	Sensitivity (tipping point)

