3.4.1.3 Sensitivity Analyses

The following analyses will be considered as sensitivity analyses:

- MI Imputation assuming MNAR utilizing CCMV-7: The same MMRM method used in the primary analysis will be applied utilizing CCMV-7 (ie, up to 7 monotone missing patterns will be used for missing value imputation as follows):

Table 5 Monotone Missing Patterns for Primary Efficacy Analysis

Timepoints where results are available	Wk1	M1	M2	M3	M4	M5	M6
Pattern 1	x	x	x	x	x	x	x
Pattern 2	x	x	x	x	x	x	.
Pattern 3	x	x	x	x	x	.	.
Pattern 4	x	x	x	x	.	.	.
Pattern 5	x	x	x
Pattern 6	x	x
Pattern 7	x

Wk1=week1; M1=month1; M2=month2; M3=month3; M4=month4; M5=month5; M6=month6;
x=observed data; .=missing data

- Tipping point analysis: A range of shifts starting from the primary analysis (CCMV) will be used in the multiple imputation of missing data assuming MNAR to identify the specific shift and treatment effect that will tip the results from statistically significant to non-significant.
- The same primary efficacy analyses described in [Section 3.4.1](#) (MMRM analysis with MI for missing value imputation) will be repeated based on non-Log transformed data.
- A MI Imputation assuming MNAR utilizing CCMV-7: The same MMRM method used in the primary analysis will be applied utilizing CCMV-7 based on non-Log transformed data.
- Tipping point analysis based on non-Log transformed data: A range of shifts starting from the primary analysis (CCMV) will be used in the multiple imputation of missing data assuming MNAR to identify the specific shift and treatment effect that will tip the results from statistically significant to non-significant.

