3.4.1.4 Supplementary Analyses

The following analyses will be considered as supplementary analyses:

- PP analysis: The same primary efficacy analyses described in [Section 3.4.1](#) (MMRM analysis with MI for missing value imputation) will be repeated based on PP analysis set.
- Completer analysis: The same primary efficacy analyses described in [Section 3.4.1](#) (MMRM analysis without missing value imputation) will be repeated on 6-Months Completer Analysis Set.

- MMRM analysis assuming MAR: The same primary endpoint analysis described above will be analyzed using MMRM assuming the missing values are missing at random (MAR; MMRM analysis without missing value imputation).
- MMRM analysis assuming MAR: The same primary endpoint analysis described above will be analyzed using MMRM assuming the missing values are missing at random (MAR; MMRM analysis without missing value imputation) based on non-Log transformed data.

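### CCMV-7 is labelled an MNAR sensitivity analysis, but as described it is an available-case (MAR) imputation with the same Month 6 donors as the primary analysis

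*SAP*

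**What the plan says.** In SAP 3.3.5 (Table 3) the primary CCMV imputation takes subjects with missing data to resemble completers of their own arm, "where completers are defined as having no missing assessments for any post-baseline visits". CCMV-7 is listed next as a sensitivity analysis: "This MI method will use all available monotone missing patterns to impute missing data assuming MNAR". Its stated purpose is: "This will relax the assumption of using only the complete cases as in the primary analysis".

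Table 4 in SAP 3.3.6 repeats the claim ("Thus this method relaxes the assumption of the primary analysis of using only completers to impute the missing data") and attaches to that row an assumption that missingness depends on what was not observed.

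SAP 3.4.1.3 puts it into operation, "The same MMRM method used in the primary analysis will be applied utilizing CCMV-7", with the seven patterns set out in Table 5, and repeats it on untransformed sSOL. SAP 3.4.2.2 and Table 6 do the same for sSE and sWASO. The bullet there does not itself say MNAR, but Table 3 covers both the primary and the key secondary endpoints. The protocol synopsis and 9.7.1.6.1 prespecify the analysis under the MNAR label: "up to 7 monotone missing patterns will be used for missing value imputation".

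Two other analyses matter here. SAP 3.4.1.4 lists as supplementary: "MMRM analysis assuming MAR: The same primary endpoint analysis described above will be analyzed using MMRM assuming the missing values are missing at random". SAP 3.3.5, 3.4.1.3, 3.4.2.2 and Section 7 plan tipping-point analyses that shift imputed Month 6 values in LEM5 and LEM10.

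**The concern.** The primary analysis assumes that subjects with missing values do as well as completers of the same arm. A sensitivity analysis labelled MNAR, and said to relax that assumption, will be read as showing what happens when the assumption fails.

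If CCMV-7 is in substance a MAR analysis, the SAP gives opposite assumptions and different standing to two nearly equivalent analyses: CCMV-7 (sensitivity, MNAR) and the MMRM (supplementary, MAR). Agreement between CCMV and CCMV-7 could then reach the study report as evidence of robustness under MNAR, which it would not be. No primary estimate, p-value or step in the testing sequence depends on CCMV-7. What is at stake is the reading of the supporting evidence.

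**Working it through.** The plan states no figure on this point, so the check sets its tables side by side and then gauges the size.

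**1. Who is in which pattern.** Section 7 of the SAP first fills intermittent gaps by MCMC so that the data are monotone. The FAS requires at least one postdose primary efficacy measurement. After that step every FAS subject falls in one of Patterns 1 to 7, and only Pattern 1 has Month 6.

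**2. Donors by visit**, read from Tables 3, 5 and 6:

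| Visit imputed | CCMV donors | CCMV-7 donors |
|---|---|---|
| Month 1 | Pattern 1 | Patterns 1-6 |
| Month 2 | Pattern 1 | Patterns 1-5 |
| Month 3 | Pattern 1 | Patterns 1-4 |
| Month 4 | Pattern 1 | Patterns 1-3 |
| Month 5 | Pattern 1 | Patterns 1-2 |
| Month 6 | Pattern 1 | Pattern 1 |

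The donor set widens at Months 1 to 5 and is unchanged at Month 6.

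**3. What each rule assumes.** Number the seven post-baseline visits 1 to 7, let D be the last observed visit, and take a subject with D = s < t.

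- CCMV: f(y_t | earlier values, D = s) = f(y_t | earlier values, D = 7).
- CCMV-7: f(y_t | earlier values, D = s) = f(y_t | earlier values, D ≥ t).

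The second line says that, given their history, subjects who have left are distributed at visit t like those still observed. Under monotone missingness that is the available-case restriction, which is MAR. At t = 7 the two lines coincide, because D ≥ 7 means D = 7.

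**4. Where the two can differ.** Pattern 2 lacks only Month 6, so its imputation is identical under both. In Patterns 3 to 7 at least one earlier visit is also imputed. Those values come from different donors and feed the Month 6 regression, so the Month 6 result can move.

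**5. Size.** The check used 200,000 subjects per arm and seven post-baseline visits on log(sSOL). It assumed a treatment effect of -0.20 at every visit, SD 0.6, correlation 0.5 + 0.5 × 0.7^lag, and monotone dropout. There were five dropout mechanisms: completely random; dependent on the last observed value or on the unseen value, each either the same or different by arm. Each was run at three dropout levels, giving 15 scenarios. Imputation was by regression within arm. All these settings are assumptions, not plan figures.

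- Month 6 regression coefficients, CCMV versus CCMV-7: maximum difference 0.
- Month 6 imputations in Pattern 2: maximum difference 0.
- Mean imputed Month 6 value in Patterns 3 to 7: moved by 0.00 to 0.07 log units.
- CCMV-7 versus the maximum-likelihood MAR estimate (unstructured covariance): equal to four decimals in all 15 scenarios.
- Treatment effect, CCMV versus CCMV-7:

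| Dropout by Month 6 | Absolute difference (log units) | Largest, relative to 0.20 |
|---|---|---|
| 16-22% | 0.000-0.004 | 0.004/0.20 = 2% |
| 25-33% | 0.000-0.009 | 0.009/0.20 = 4.5% |
| 42-52% | 0.000-0.028 | 0.028/0.20 = 14% |

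The movement went in either direction, depending on the dropout mechanism.

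**The case against.** The best defence has three parts.

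First, CCMV-7 does change the assumption. CCMV is not MAR, so going from CCMV to MAR is a real move, and the SAP's statement that completer-only imputation is relaxed is true for Months 1 to 5. This stands. A reader might infer from the shared Month 6 donors that CCMV-7 cannot test the primary result, or that agreement is built in. The documents do not support that: earlier imputed visits feed the Month 6 regression, and the check shows shifts of up to 0.028 log units.

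Second, the assumption about dropouts is already challenged elsewhere. The tipping-point analyses start from CCMV and from MAR, shift imputed Month 6 values in LEM5 and LEM10 only, and increase the shift until significance is lost. The CCMV-based ones cover log and raw sSOL, sSE and sWASO. This also stands, so it would be wrong to say the primary result goes untested. Two limits remain: the SAP gives no criterion for a plausible shift, and no planned analysis gives an effect estimate under one concrete, less favourable assumption for active-arm dropouts.

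Third, a reader might go on to infer that the primary estimate is off by some amount. That would be a criticism of CCMV itself, and it would depend on how much is truly missing. The protocol encourages subjects who stop drug to continue the diary and visits, and SAP 3.4.1 uses those data. The 50% discontinuation at Month 6 in the sample-size sections is an upper bound in a safety-exposure argument, not a forecast of missing Month 6 values.

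**Conclusion.** CCMV-7 is mislabelled. The donor result follows directly from SAP Tables 3, 5 and 6, and the MAR result follows from monotone missingness with all seven patterns used. Neither depends on the simulation. The analysis is close to the supplementary MAR MMRM. It would differ from it through the extra imputation covariates, multiple-imputation noise and, for sSE, truncation.

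As a check on the primary analysis it is weak and stops at MAR: dropouts' unseen Month 6 values may differ from completers' only through their observed history. The sizes (at most 0.004 log units at 16-22% dropout, 0.028 at 42-52%) rest on the assumed covariance and dropout models. The check imputed within arm, whereas the sample code carries treatment as a covariate; this does not alter the donor table. CCMV-7 was read from the SAP's description and tables, because Section 7 gives code only for CCMV.

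The consequence is limited to interpretation. Agreement between CCMV-7 and the primary result should not be reported as robustness under MNAR. The primary analysis stands as planned.

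**What to change.** Before Period 1 is unblinded:

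- In SAP 3.3.5 (Table 3), 3.3.6 (Table 4), 3.4.1.3 and 3.4.2.2, keep CCMV-7 but call it an available-case/MAR analysis. Correct the MNAR label and the sentences on relaxing the assumption, to say that donors widen for Months 1 to 5 and are unchanged for Month 6. Place it beside the MAR MMRM and note the overlap.
- Make the same wording change in the protocol synopsis and 9.7.1.6.1. CCMV-7 is prespecified there, which is a reason to keep it rather than replace it.
- Name the tipping point as the MNAR sensitivity analysis.
- Add the CCMV-7 code to Section 7.
- Add, without substituting for anything, an imputation of missing LEM5 and LEM10 values from placebo donors for sSOL, sSE and sWASO. It uses the existing MNAR step with `MODELOBS` restricted to placebo. Treatment must leave that step's `VAR` list, since it is constant among placebo donors.

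The cost is text edits in both documents and one further analysis per endpoint, which is likely to give a smaller estimate than the primary. The primary analysis, alpha and data collection do not change.
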